10.1.4 Single Agent Maintenance Phase

After completion of 6 cycles of combination chemotherapy cycles or after discontinuation of the chemotherapy for any other reason apart from progression, the patients will continue to receive CetuGEX™ alone or cetuximab alone, respectively. Single-agent maintenance therapy will be continued until progression of disease or limiting toxicity.

On **Day 1 of each week** of the single-agent maintenance phase, the following will be performed or assessed:

- Physical examination.

- Vital signs (blood pressure, heart rate and body temperature) and body weight and BMI.
- 12-lead ECG (every 6 weeks after randomization).
- Record ECOG performance status.
- Evaluation of tumor size by CT or MRI (to be performed pre-dose, every 6 weeks within the first 18 weeks after randomization, and every 8 weeks thereafter; same equipment and type of imaging as used at Screening is required throughout the study).
- Blood and urine sampling for safety laboratory (hematology, coagulation panel, blood chemistry and urinalysis; to be performed every 6 weeks after randomization).
- QoL questionnaires EORTC-QLQ-C30 and EORTC-QLQ-H&N35 (to be performed prior to any other assessments; to be performed 18 weeks after date of randomization. In case of premature discontinuation of combination treatment, also to be performed 6 weeks and 12 weeks after randomization, as applicable).
- Pregnancy test for female patients of childbearing potential (will be performed only on the first week of maintenance therapy pre-dose).
- Blood sampling for ADA testing (only for patients receiving CetuGEX™; only to be performed 1, 3 and 9 weeks after randomization, pre-dose, if chemotherapy was discontinued prematurely).
- Blood sampling for PK assessments (only for patients receiving CetuGEX™; only to be performed until the 10th infusion of CetuGEX™, if chemotherapy was discontinued prematurely).
- Blood sampling for additional PK assessments (only for a subgroup of approximately 30 patients receiving CetuGEX™; only to be performed until the 11th infusion of CetuGEX™ [pre-dose], if chemotherapy was discontinued prematurely).
- Administration of CetuGEX™/cetuximab (time window for infusion: ± 1 day calculated from the previous infusion).
- Drug accountability.
- Recording of concomitant medication.
- Assessment of AEs.

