10.3.2 Quality of Life Measures

To assess the QoL of each patient, patient-reported disease-related symptoms and health related QoL will be measured using the EORTC-QLQ-C30 questionnaire and the head and neck module (H&N35; according to the availability of the validated translations). Patients will be required to complete the questionnaires prior to any other assessments on Day 0 (CetuGEX™ patients only) and Day 1 of Cycle 1 (cetuximab patients only), respectively, as well as on Day 1 of Cycles 3 and 5 (i.e., 6 weeks and 12 weeks after randomization), 18 weeks after randomization and 28 (+ 2) days after last treatment administration (Safety Visit).

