Abbreviations: BMI = body mass index, CT = computed tomography, ECHO = echocardiogram, ECOG = Eastern Cooperative Oncology Group, EGFR = epidermal growth factor receptor, FE = Final Examination, HPV = human papilloma virus, IWRS = interactive web response system, MRI = magnetic resonance imaging, MUGA = Multiple Gated Acquisition, PK = pharmacokinetics, SCCHN = squamous cell carcinoma of the head and neck, 5-FU = 5-fluorouracil, W = week.

* Day 0 only applies for patients randomized to receive CetuGEX™.

- 1 The Safety Follow-Up Visit constitutes the Final Examination Visit for the patients treated with study medication until progression of disease.
- 2 As soon as progression of disease is detected, FE assessments will be performed for all patients who prematurely discontinued study treatment. For patients withdrawing prematurely from the complete study, the Final Examination will be performed at the date of withdrawal.
- 3 Will be performed quarterly by phone calls for at least 24 months after randomization of last patient.
- 4 To be performed pre-dose, as applicable.
- 5 To be performed only for patients receiving cetuximab, only on Day 1 of Cycle 1.
- 6 The investigator may contact the IWRS for randomization within 1 to 3 days prior to first infusion.

- 7 To be performed in Cycle 2 and every following cycle; To be performed in Cycle 1 only for patients receiving cetuximab.
- 8 Height will be measured only at screening.
- 9 Only to be performed, if not done within 7 days prior randomization.
- 10 To be performed every 6 weeks after randomization (i.e., Day 1 of Cycles 3 and 5, and every 6 weeks thereafter).
- 11 To be performed every 6 weeks within the first 18 weeks after randomization, and every 8 weeks thereafter.
- 12 To be performed every 6 weeks after randomization.
- 13 Pre-existing tumor-tissue samples will be sent to laboratory once patient was randomized; remaining tumor-tissue needs to be stored for further analysis
- 14 To be performed only in a subset of approximately 30 patients per treatment arm.
- 15 To be performed pre-dose, 1h after start of infusion and at the end of the first infusion.
- 16 To be performed pre-dose, at the start of the highest infusion rate, 1 h after start of the highest infusion rate and at the end of infusion on Day 1 of Cycle 1; pre-dose, 1 h after start of infusion and at the end of infusion on Day 1 of Cycle 2.

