- 17 To be performed pre-dose, 1 h after start of infusion and at the end of infusion on Cycle 1, only.
- 18 To be performed pre-dose, only on Day 1 of Cycle 1 for patients receiving cetuximab.
- 19 To be performed pre-dose, only on Day 8 of Cycle 2.
- 20 To be performed only for patients receiving CetuGEX™.
- 21 To be performed pre-dose, on Day 1 of Cycles 2 and 4 only.
- 22 To be performed pre-dose, on Day 8 of Cycle 1 only.
- 23 Only in case the patient will enter the study, this blood sample might be used at a later time point for further analyses like FCγRII status.
- 24 To be performed pre-dose, only on the first week of maintenance therapy.
- 25 Blood sampling for PK prior to the start of infusion and at the end of infusion, on Day 1 of Cycles 1 to 4, only.
- 26 For a subgroup of approximately 30 patients only: Additional blood sampling for PK as detailed in Appendix B.
- 27 Blood sampling for PK prior to start of infusion and after the end of infusion: in Cycles 1 to 3 for all patients; in Cycle 4 only for a subgroup of approximately 30 patients, prior to start of infusion; all PK samplings as detailed in Appendix B.
- 28 Blood sampling for PK prior to start of infusion and at the end of infusion, only in Cycle 1 to 3, for all patients.
- 29 Blood sampling for PK prior to start of infusion and after the end of infusion until 10th infusion after randomization, if combination therapy was discontinued prematurely.
- 30 To be performed 18 weeks after randomization. In case combination therapy was discontinued prematurely, also 6 and 12 weeks after randomization, as applicable.
- 31 For Cycle 1, cisplatin is mandatory. Change to carboplatin in subsequent cycles might be accepted in case of toxicity of cisplatin.
- 32 HPV status will be assessed at a central laboratory, either at randomization or at a later time point. A tumor-tissue sample provided will be used for evaluation.
- 33 Please note that creatinine clearance needs to be assessed at screening unless previous results not older than 6 weeks are available.
- 34 Site visits on days 2 to 4 are only obligatory for patients either included in the PK subgroup or if they have no transportable pump for 5-FU administrations. Assessment of vital signs and records of drug accountability, adverse events, and concomitant medication will only be performed for patients visiting the site.
- 35 To be performed pre-dose, 1, 3 and 9 weeks after randomization, if combination therapy was discontinued prematurely.

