##### Single-agent maintenance phase

After completion or discontinuation of combination chemotherapy for any other reason than progression, the treatment will be followed by maintenance therapy with CetuGEX™ alone or cetuximab alone, respectively. Single-agent maintenance therapy will be continued until progression of disease or limiting toxicity.

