##### Follow-up

A Safety Visit must be performed 28 (+2) days after the last administration of the study drug for all randomized patients. In case of treatment discontinuation due to reasons other

than disease progression, patients will stay on the regular study schedule until disease progression is documented and will then attend a Final Examination Visit. In case of treatment discontinuation due to disease progression, the Safety Visit is identical to the Final Examination Visit.

After the Final Examination, patients will be followed-up by quarterly phone calls until death or for a maximum duration of 24 months after randomization of the last patient for assessment of overall survival.

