In addition, for the QLQ-C30 scales, the difference with respect to baseline will be classified as  $\leq -10$ ,  $-10 - 10$ ,  $\geq 10$ . The rates of patients within these ranges will be presented by treatment group and visit. The time from randomization to the first occurrence of a deterioration of at least 10 points ( $\leq -10$  for global and functional scales,  $\geq 10$  for symptom scales) will be analyzed by Kaplan-Meier methods. Patients without occurrence of deterioration will be censored at the last assessment. The estimate of the quartiles of the time to deterioration as well as the associated 95%-confidence intervals will be tabulated by treatment arm together with the p-value of a log rank test.

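### After week 18 the next scheduled QoL form is the Safety Visit, so a later deterioration is dated by treatment length and Kaplan-Meier quartiles beyond 4.1 months are too long

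*SAP*

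**What the plan says.** **Collection.** Protocol 10.3.2 has forms at baseline, on Day 1 of Cycles 3 and 5 (weeks 6 and 12), and then "18 weeks after randomization and 28 (+ 2) days after last treatment administration (Safety Visit". The maintenance-phase list in Protocol 10.1.4 has QoL "to be performed 18 weeks after date of randomization", with weeks 6 and 12 added only if combination treatment stopped early. Footnote 30 of the Schedule of Events (18.1), on the maintenance cell, agrees: "To be performed 18 weeks after randomization. In case combination therapy was discontinued prematurely, also 6 and 12 weeks after randomization, as applicable". The Final Examination list and the quarterly calls in Protocol 10.1.5 contain no QoL.

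Footnote 10, on the Day 1 combination-phase QoL cell, reads differently: "To be performed every 6 weeks after randomization (i.e., Day 1 of Cycles 3 and 5, and every 6 weeks thereafter".

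**Treatment length.** SAP 3.1 says "Single-agent maintenance therapy will be continued until progression of disease or limiting toxicity". For patients who stop earlier for another reason, "patients will stay on the regular study schedule until disease progression is documented". After week 18 that schedule holds no further QoL form apart from the Safety Visit.

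**Analysis.** SAP 11.6 takes "The time from randomization to the first occurrence of a deterioration of at least 10 points" for each QLQ-C30 scale. It reports Kaplan-Meier quartiles with 95% confidence intervals and a log-rank p-value by arm. On censoring it says "Patients without occurrence of deterioration will be censored at the last assessment". It has no rule for the gap after week 18 and no interval-censored method.

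**The concern.** A worsening can be dated only at a form that shows it. Up to week 18 the forms are six weeks apart, so the dating error is modest and similar in both arms. After week 18 the next form comes when treatment has ended. A patient who worsens at week 22 and stays on treatment until month 12 is recorded as worsening at month 12.9.

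That date depends largely on progression, the primary endpoint. If CetuGEX prolongs PFS as planned, its patients complete their next form later. Their late worsening is then dated later even if QoL is the same in both arms. The reported quartiles and the between-arm p-value would partly restate PFS as a QoL finding.

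**Working it through.** **1. Planning model.** From SAP 5: median PFS 5.6 and 8.4 months, two-sided 0.05, power 80%, 1:1. Schoenfeld: D = 4(1.960 + 0.842)² / (ln(5.6/8.4))² = 4 × 7.849 / 0.1644 = 191, against the stated 192. Exponential PFS with these medians therefore represents the plan fairly. The documents give no planning figure for time to deterioration.

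**2. Who is exposed to the gap.** Week 18 is 126 / 30.4375 = 4.14 months (conversion factor from SAP 7.2). Progression-free then, exp(−ln 2 × 4.14 / m):
- cetuximab (m = 5.6): 59.9%
- CetuGEX (m = 8.4): 71.1%

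Most patients would therefore next complete a form about 28 days after treatment ends. With treatment ending at month 12, the form falls at 12 + 28/30.4375 = 12.9 months, leaving a gap from 4.1 to 12.9.

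**3. Medians, worsening independent of progression.** Simulation of 200,000 patients per arm. Assumptions not in the documents: exponential onset, equal in both arms; worsening lasts; treatment stops at progression; all Safety Visits done. Forms at weeks 6, 12 and 18 while on treatment, plus the Safety Visit; cut-off 12 to 36 months after randomization; SAP event and censoring rules. The last column adds forms every 8 weeks after week 18, purely as a comparison to isolate the gap.

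| True median (months) | Planned schedule, cetuximab | Planned schedule, CetuGEX | Forms every 8 weeks after week 18 |
|---|---|---|---|
| 2 | 2.8 | 2.8 | 2.8 |
| 4 | 4.1 | 4.1 | 4.1 |
| 5 | 7.0 | 7.7 | 6.0 |
| 6 | 9.1 | 10.0 | 6.0 |
| 8 | 11.5 | 12.5 | 7.8 |
| 12 | 14.4 | 15.7 | 11.5 |

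For true medians of 5 to 12 months the excess is about 2.0 to 3.5 months (cetuximab) and 2.7 to 4.5 months (CetuGEX). Up to 4 months the late gap does not matter. With 60% of Safety Visits done, the medians change little.

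**4. Other quartiles, same assumptions.**
- Upper: with a true median of 4 months the true upper quartile is 8.0 and is reported as about 12.2 (cetuximab) and 13.4 (CetuGEX), although the median is barely affected.
- Lower: with a true median of 6 the true lower quartile is 6 × ln(4/3) / ln 2 = 2.5 and is reported as 2.8 in both arms, which is the week-12 form (84 / 30.4375 = 2.76).

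**5. Worsening at progression at the latest.** The Kaplan-Meier median is 0.5 to 1.8 months above the truth, but adding 8-weekly forms does not lower it (for example 5.9 as planned, 6.0 with added forms). Here the late gap is not the cause.

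**6. Log-rank test.** Equal deterioration in both arms independent of progression, PFS 5.6 against 8.4 months, 120 per arm, 1,500 trials per case, true medians 3 to 12 months, 60% or 100% of Safety Visits done:
- Planned schedule: two-sided rejection 5.4% to 7.3%; false results favouring CetuGEX 4.5% to 6.6% (nominal 2.5%).
- Forms every 8 weeks after week 18: 4.5% to 5.9%, and 3.1% to 3.9%.

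The Monte Carlo standard error is √(0.05 × 0.95 / 1500) = 0.6 points two-sided and √(0.025 × 0.975 / 1500) = 0.4 points one-sided. The low end of the two-sided range is within noise; the one-sided excess is not.

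**7. Which week-18 restriction is safe.** Let worsening come at the earlier of progression and an independent onset with median 6 months. The true deterioration-free rate at week 18 is exp(−ln 2 × 4.14 × (1/6 + 1/5.6)) = 37% for cetuximab, and 44% with 8.4 in place of 5.6.
- Dropping all Safety Visits leaves only forms completed before progression: exp(−ln 2 × 4.14 / 6) = 62% in both arms. Both rates are overstated and a true difference disappears.
- Keeping Safety Visits up to week 18 misses only patients who progress in weeks 14 to 18 without worsening by week 12. Cetuximab: (67.1% − 59.9%) × exp(−ln 2 × 2.76 / 6) = 7.2% × 0.727 = 5.2 points. CetuGEX: (76.7% − 71.1%) × 0.727 = 4.1 points. The rates become 42% and 48%.

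**The case against.** **Early worsening may dominate.** The event is a single unconfirmed 10-point change during up to six cycles of platinum and 5-FU, so many scales may have their median before week 18. This stands for the median. It does not clear the upper quartile, which SAP 11.6 also tabulates for all 15 QLQ-C30 scales.

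**Independence is the unfavourable assumption.** For a cancer symptom scale, worsening may follow progression. Step 5 shows that the late gap is then harmless to the median, and later worsening in the longer-PFS arm would be a real effect. This stands. A reader might infer that the medians are bound to be too long, or that any QoL advantage for CetuGEX would be an artefact. The documents give no deterioration rate or mechanism, so they support neither.

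**Not every quartile is affected.** A reader might infer that all quartiles are wrong once fewer than half have worsened by week 18. Step 4 shows the lower quartile can still sit on the 6-weekly grid.

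**The censoring sentence is not the cause.** Late dates arise because an event is placed at the first form that shows it. The censoring rule acts separately: patients still on treatment at cut-off are censored at week 18 at the latest, which may itself be informative.

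**The schedule may be denser than claimed.** Footnote 10 can be read as continuing forms every six weeks. Footnote 30 governs the maintenance cell, however, and Protocol 10.1.4 and 10.3.2 agree with it. What remains is an inconsistency to resolve.

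**Treatment can end for other reasons.** Toxicity or dosing delay can also end it, so the Safety Visit date is closely tied to PFS without being fixed by it.

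**Conclusion.** The point holds in conditional form. A deterioration that first arises after week 18 is dated at about treatment end plus 28 days, so Kaplan-Meier quartiles beyond 4.1 months are too long: most often the upper quartile, and the median when fewer than half have worsened by week 18.

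If worsening is independent of progression, true medians of 5 to 12 months are overstated by about 2 to 3.5 months (cetuximab) and 2.7 to 4.5 months (CetuGEX). The log-rank test then tilts mildly toward the arm with longer PFS. These sizes rest on exponential times, lasting worsening, treatment stopping at progression and the planning PFS medians. With worsening at progression at the latest, the late gap does not lengthen the median.

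QoL is a secondary endpoint. The primary PFS test, the 192-event target, and the QoL score changes and response classes by visit are unaffected. The correction is still worth making, because a pre-specified between-arm p-value is involved and SAP wording is enough.

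**What to change.** In SAP 11.6:
- Base the between-arm comparison of time to deterioration on all QoL forms up to week 18, including Safety Visits that fall by then. State the visit window, censor administratively at week 18, and report the week-18 deterioration-free rate by arm.
- Alternatively, analyse full follow-up with an interval-censored method, each event lying between the last form without deterioration and the first with it. Safety Visit timing depends on progression, so this needs caution if worsening is linked to progression.
- Report Safety Visit scores after week 18 descriptively, and do not report ordinary Kaplan-Meier quartiles beyond week 18.

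In the protocol, reconcile footnote 10 of the Schedule of Events with sections 10.1.4 and 10.3.2 and footnote 30.

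Cost: SAP wording and one footnote, with no new data. The restricted analysis gives no late deterioration times, which the schedule measures poorly anyway. The interval-censored analysis is less precise and takes a little more work.

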## **12. CHANGES COMPARED TO THE CLINICAL TRIAL PROTOCOL**

All planned statistical analyses are in agreement with the clinical trial protocol.

## **13. REPORTING CONVENTIONS**

The following reporting conventions will be adopted for the presentation of study data. These conventions will enhance the review process and help to standardize presentation with common notations.

### **13.1 General Reporting Conventions**

- All tables and data listings will be developed in Landscape Orientation, unless presented as part of the text in a CSR.
- Figures will be presented in landscape orientation, unless presented as part of the text in a CSR.
- Legends will be used for all figures with more than one variable or item

displayed.

- Figures will be in black and white, unless color figures have been identified as useful for discriminating presentation in the figure. Lines in figures should be wide enough to view the line after being photocopied.
- Specialized text styles, such as bolding, italics, borders, shading, superscripted and subscripted text will not be used in tables, figures, and data listings unless they add significant value to the table, figure, or data listing.
- Only standard keyboard characters should be used in tables and data listings. Special characters, such as non-printable control characters, printer specific, or font specific characters, will not be used on a table, figure, or data listing. Hexadecimal character representations are allowed (e.g.  $\mu$ ,  $\alpha$ ,  $\beta$ ).
- All titles will be centered on a page. The ICH numbering convention is to be used for all tables, listings, and graphs.
- All footnotes will be left justified and at the bottom of a page. Footnotes must be present on the page where they are first referenced. Footnotes should be used sparingly and must add value to the table, figure, or data listing. If more than four footnote lines are planned, then a cover page may be used to display footnotes.
- Missing values for both numeric and character variables will be presented as blanks in a table or data listing. A zero (0) may be used if appropriate to identify when the frequency of a variable is not observed.
- All date values will be presented as DDMMYYYY (e.g., 29AUG2001) format. A four-digit year is preferred for all dates.
- All observed time values will be presented using a 24-hour clock HH:MM:SS format (e.g., 01:35:45 or 11:26). Seconds should only be reported if they were measured as part of the study.
- Time durations will be reported in HH:MM:SS notation. The use of decimal notation to present (display) time durations should be avoided (e.g. 0.083h = 5m) unless it is necessary to show the computation of time differences in a table, figure, or data listing, in which case both notations may be used to display the time duration.
- All tables, figure, and data listings will have the name of the program and a date stamp on the bottom of each output.

### 13.2 Population Summary Conventions

- Population(s) represented on the tables or data listings will be clearly identified in the last title of the Table as “Population: <name of population>” and will be identical in name to that identified in the protocol or SAP.
- Consistent terminology will be used to define and identify a population. Common nomenclature may include (a) Full Analysis or ITT, (b) All Patients, (c) PP or Per-Protocol, (d) Efficacy, (e) Safety, or (f) Pharmacokinetic.

- Sub-population(s) or special population(s) descriptions will provide sufficient detail to ensure comprehension of the population (e.g., ITT Females, Per-Protocol Males >60 years of age) used for analysis in a table or figure.
- Population sizes may be presented for each treatment or dosing category as totals in the column header as (N=xxxx), where appropriate.
- Population sizes shown with summary statistics are the samples sizes (n) of patients with non-missing values.
- All population summaries for continuous variables will include: N, mean, standard deviation, minimum, and maximum. Other summaries (e.g. number missing, median, quartiles, 5%, 95% intervals, CV or %CV) may be used as appropriate.
- All percentages are rounded and reported to a single decimal point (xx.x%).
- Population summaries that include p-values will report the p-value to three decimal places with a leading zero (0.001). All p-values reported on default output from statistical software (i.e., SAS® Software) may be reported at the default level of precision. P-values <0.001 should be reported as <0.001 not 0.000.

